4.3. Childbearing Potential

A subject of childbearing potential is anyone born female who has experienced menarche and who has not undergone surgical sterilization (eg, hysterectomy, bilateral salpingectomy, bilateral oophorectomy) or has not completed menopause. Menopause is defined clinically as 12 months of amenorrhea in a subject over age 45 in the absence of other biological, physiological, or pharmacological causes.

A subject who can father children is anyone born male who has testes and who has not undergone surgical sterilization (eg, vasectomy followed by a clinical test proving that the procedure was effective).

4.4. Removal of Subjects From Therapy or Assessment

Seagen Inc. or their designee must be notified if a subject is discontinued from study treatment or withdrawn from the study. The reason(s) for discontinuation/withdrawal must be documented in the subject's medical records.

4.4.1. Discontinuation of Study Treatment

A subject's study treatment may be discontinued for any of the following reasons:

- Progressive disease (PD)
- AE
- Pregnancy
- Investigator decision
- Subject decision, non-AE

Note: Ensure that subjects who decide to stop treatment **because of an AE** are not included in this rationale.

- Study or cohort termination by sponsor
- Other, non-AE

Subjects who discontinue from study treatment will remain on study for follow-up unless they withdraw consent.

For Part C Arm 2 and Arm 3:

Patients who discontinue pembrolizumab may continue to receive LV with medical monitor approval. Similarly, patients that discontinue LV may continue to receive pembrolizumab with medical monitor approval. See Sections [5.2.4.3](#) and [5.3](#) for details.

Administration of pembrolizumab is limited to 35 cycles (approximately 2 years). The number of administrations is calculated starting with the first dose of pembrolizumab.

4.4.2. Subject Withdrawal From Study

Any subject may be withdrawn from the study for any of the following reasons:

- Subject withdrawal of consent
- Study or cohort termination by sponsor
- Lost to follow-up
- Death
- Other

5. TREATMENTS

5.1. Treatments Administered

Part A (q3wk dosing): LV will be administered at a dose of 2.5 mg/kg as a 30-minute IV infusion on Day 1 of each 21-day cycle. For subjects weighing more than 100 kg, dosing will be capped at 250 mg per infusion. Any subject receiving >200 mg LV per infusion (weight >80 kg) is required to receive prophylactic G-CSF.

Part B (q1wk dosing): LV will be administered at a dose of 1.0 or 1.25 mg/kg as a 30-minute IV infusion on Day 1, Day 8, and Day 15 of each 21-day cycle. The maximum dose will be 200 mg per infusion.

Part C (LV monotherapy or LV plus pembrolizumab combination): LV will be administered at a dose of 1.5 mg/kg (Arms 1 and 2) as a 30-minute IV infusion on Day 1 and Day 8 but not Day 15 of each 21-day cycle (2q3wk). The maximum dose will be 200 mg per infusion. For Arm 3, LV will be administered at a dose of 1.25 mg/kg as a 30-minute IV infusion on Day 1, Day 8, and Day 15 of each 21-day cycle (q1wk). The maximum dose will be 200 mg per infusion. For Arm 2 and Arm 3, pembrolizumab will be administered at a dose of 200 mg approximately 60–90 minutes after LV as a 30-minute IV infusion on Day 1 of each 21-day cycle (q3wk).

5.2. Investigational Study Drug: LV

Detailed information describing the preparation, administration, and storage of LV is located in the Pharmacy Instructions.

5.2.1. Description

LV is a sterile, preservative-free, white to off-white lyophilized cake or powder for reconstitution for IV administration. LV is supplied by Seagen Inc. in single-use glass vials. Each drug product vial contains LV for injection, trehalose, histidine, and polysorbate 80. Drug product vials are labeled with a nominal content of 40 mg/vial. Each vial contains 45 mg of LV. Enough overfill is included to allow for 40 mg of LV to be withdrawn for use.

When reconstituted with 8.8 mL water for injection (WFI), United States Pharmacopeia (USP) grade or equivalent, the concentration of reconstituted LV product is 5 mg/mL. The reconstituted drug product is a clear to slightly opalescent, colorless to light yellow solution with no visible particulate matter. The pH is approximately 6.0. The reconstituted solution is subsequently diluted in sterile 0.9% Sodium Chloride for Injection, USP grade or equivalent, for IV administration.

5.2.2. Method of Procurement

LV will be provided by the sponsor or designee.

5.2.3. Dose and Administration

LV is administered by IV infusion given over approximately 30 minutes. LV must not be administered as an IV push or bolus. In the absence of infusion-related reactions (IRR), the infusion rate for all subjects should be calculated in order to achieve a 30-minute infusion period.

However, given the variability of infusion pumps from site to site, a window between -5 minutes and +10 minutes is permitted (i.e., infusion time is 30 minutes -5 min/+10 min).

LV can be administered via central venous access line (preferred) or peripheral IV. Clinical site staff should monitor the infusion site closely for redness, swelling, pain, and infection during and at any time after administration. Advise subjects to report redness or discomfort promptly at the time of administration or after infusion. The IV bag containing LV should not be mixed with other medications.

Dosing is based on the subject's actual body weight at the beginning of each cycle.

Detailed instructions for dose preparation are provided in the Pharmacy Instructions.

Part A (q3wk dosing): LV at a dose of 2.5 mg/kg (maximum dose of 250 mg per infusion) will be administered on Day 1 of each 21-day cycle by IV infusion given over approximately 30 minutes. **For subjects weighing greater than 100 kg, dose calculations will be based on 100 kg for these individuals (including dose reductions).** Rounding is permissible within 1 mg of nominal dose. Any subject receiving >200 mg LV per infusion (weight >80 kg) is required to receive prophylactic G-CSF.

Part B (q1wk dosing): LV at a dose of 1.0 or 1.25 mg/kg will be administered on Day 1, Day 8, and Day 15 of each 21-day cycle. The maximum dose will be 200 mg per infusion.

Part C (2q3wk or q1wk dosing): LV at a dose of 1.5 mg/kg will be administered on Day 1 and Day 8 but not Day 15 of each 21-day cycle (2q3wk) for Arm 1 and Arm 2. LV at a dose of 1.25 mg/kg will be administered on Day 1, Day 8, and Day 15 of each 21-day cycle (q1wk) for Arm 3. The maximum dose of LV for all 3 arms will be 200 mg per infusion. For Arm 2 and Arm 3, pembrolizumab infusion must start approximately 60–90 minutes after administration of LV (see Section 5.3.3).

5.2.3.1. Dosing Criteria

The following laboratory criteria must be met on Day 1 of each cycle prior to LV administration:

- Neutrophil count $\geq 1000/\mu\text{L}$ (\leq Grade 2)
- Aspartate aminotransferase \leq Grade 2
- ALT \leq Grade 2
- Total bilirubin \leq Grade 2

In Part B and C, neutrophil count must be $\geq 1000/\mu\text{L}$ (\leq Grade 2) prior to LV administration on Day 8 and Day 15 (if receiving q1wk dosing) of each cycle.

If the above criteria are not met on the day of dosing, hold the LV dose until the criteria are met. In addition, hold LV dosing for subjects with \geq Grade 2 peripheral neuropathy (see Table 10).

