6.3.3. Treatment Cycle (Day 1 to Day 21)

6.3.3.1. Day 1

If baseline visit activities occur within 3 days prior to C1 Day 1, the following assessments do not need to be repeated at the C1 Day 1 visit:

- Physical exam (Section [7.6.4](#)) including weight
- ECOG performance status ([Appendix J](#))
- CBC with differential
- Serum chemistry panel and liver function tests
- Pregnancy test
- PSA test for prostate cancer subjects

Predose

- Confirm subject meets dosing criteria (Section [5.2.3.1](#))
- Physical exam (Section [7.6.4](#)), including weight
- Pregnancy test (serum or urine) for subjects of childbearing potential (see Section [7.6.5](#)) – does not need to be repeated if it has been performed within 3 days prior to administration of LV
- ECOG performance status ([Appendix J](#))
- Random blood glucose to be collected prior to dosing on Day 1 of each 21-day cycle (see Section [5.6](#); results to be submitted to iRIS)
- CBC with differential (see Section [7.6.3](#); results to be submitted to iRIS)
- Serum chemistry panel and liver function tests (see Section [7.6.3](#); results to be submitted to iRIS)
- Vital signs (within 60 minutes prior to the start of LV infusion, see Section [7.6.2](#))
- Blood samples for PK and ATA assessment (C1-C5 and every 5 cycles thereafter, see Section [7.3](#) for time points)
- Blood samples for biomarker assessment (C1 to C6 only; see Section [7.4.1](#))
- Review CT/MRI, if applicable (see Section [7.2](#))
- For prostate cancer subjects:
 - Review bone scan, if applicable (see Section [7.2](#))
 - PSA test (see Section [7.6.3](#))
- LV administration (a +2 day dosing window is allowed for subsequent dosing within a cycle; see Section [5.2.3](#)). For nonclinical events requiring skipping a dose(s), must consult with and obtain approval by sponsor medical monitor. At least 7 days must elapse between administrations of LV.

Postdose

- Blood samples for postdose PK assessment (C1-C5 and every 5 cycles thereafter, see Section 7.3 for time points)
- Vital signs (within 30 minutes of ending each infusion, and during infusion as clinically indicated; see Section 7.6.2)
- If available, submit tumor tissue samples for biomarker analysis as soon as reasonably possible after the subject has met all eligibility requirements (C1 only; see Section 7.4.2)

6.3.3.2. Day 3

- Blood samples for PK assessment (visit window may be +1 day; C1 and C4 only, see Section 7.3)

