6.3.3.3. Day 8 (± 2 days)

Predose

- Confirm subject meets dosing criteria (Section 5.2.3.1)
- Physical exam (Section 7.6.4) (C1 only)
- CBC with differential (see Section 7.6.3; results to be submitted to iRIS), Cycles 1 and 2 only
- Serum chemistry panel and liver function tests (see Section 7.6.3; results to be submitted to iRIS), Cycles 1 and 2 only
- Random blood glucose in Cycles 1 and 2. Following C2, random blood glucose may be collected as indicated in subjects at risk for hyperglycemia. (see Section 5.6; results to be submitted to iRIS)
- Vital signs (within 60 minutes prior to the start of LV infusion, see Section 7.6.2)
- Blood samples for PK assessment (C1 and C4 only; see Section 7.3 for time points)
- LV administration (a +2 day dosing window is allowed for subsequent dosing within a cycle; see Section 5.2.3). For nonclinical events requiring skipping a dose(s), must consult with and obtain approval by sponsor medical monitor. At least 7 days must elapse between administrations of LV.

Postdose

- Vital signs (within 30 minutes of ending each infusion, and during infusion as clinically indicated; see Section 7.6.2)
- Blood samples for PK assessment (C1 and C4 only; see Section 7.3 for time points)

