- CBC with differential (see Section 7.6.3; results to be submitted to iRIS)
- Serum chemistry panel and liver function tests (see Section 7.6.3; results to be submitted to iRIS)
- **Arm 2 and Arm 3:** Thyroid function tests (detailed in Section 7.6.3); to include thyroid-stimulating hormone (TSH), T3 or free T3, and free T4). Day 1 of each odd-numbered cycle only (i.e. Cycles 1, 3, 5, 7, etc).
- Vital signs:
 - **Arm 1:** within 60 minutes prior to the start of LV infusion, see Section 7.6.2
 - **Arm 2 and Arm 3:** within 60 minutes prior to LV infusion, within 60 minutes prior to pembrolizumab infusion, see Section 7.6.2
- Blood samples for PK and ATA assessment (C1 to C5 and every 5 cycles thereafter, see Section 7.3 for time points)
- Blood samples for biomarker assessment (C1 to C6 only; see Section 7.4.1)
- Review CT/MRI, if applicable (see Section 7.2)
- **Arm 1, Arm 2, and Arm 3:** LV administration (a +4 day dosing window for Arm 1 and Arm 2 and a +2 day window for Arm 3) is allowed for subsequent dosing within a cycle; see Sections 5.2.3, 5.2.4.2, and 5.2.4.3. For nonclinical events requiring skipping a dose(s), must consult with and obtain approval by sponsor medical monitor. At least 7 days must elapse between administrations of LV.
- **Arm 2 and Arm 3:** Pembrolizumab will be administered 60–90 minutes following LV. For nonclinical events requiring skipping a dose(s), must consult with and obtain approval by sponsor medical monitor.

Postdose

- Vital signs:
 - **Arm 1:** within 30 minutes of ending each LV infusion, and during infusion as clinically indicated; see Section 7.6.2
 - **Arm 2 and Arm 3:** within 2 hours of ending each infusion, and during infusion/s as clinically indicated; see Section 7.6.2
- Blood samples for PK assessment (see Section 7.3 for time points)

6.4.3.2. Day 3

- Blood samples for PK assessment (visit window may be +1 day; C1 and C4 only, see Section 7.3)

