APPENDIX C. SCHEDULE OF EVENTS FOR TREATMENT (Q1WK DOSING; PART B)

	Assessment	Enrollment	Cycle 1				Cycle 2+				EOT	F/U
			D1	D3	D8	D15	D1	D3	D8	D15		
	Day	Within 7D of 1st dose	± 2d ^b	+ 1d	± 2d	± 2d	± 2d	+ 1d	± 2d	± 2d	Within 30–37D of last dose ^a	Every 6 or 12 weeks
	Visit window		± 2d ^b	+ 1d	± 2d	± 2d	± 2d	+ 1d	± 2d	± 2d		± 3d or ± 7d
	Confirm subject meets dosing criteria		X		X	X	X		X	X		
	PSA test ^c		X ^d				X				X	X
Treatment	LV administration	Submit eligibility confirmation to sponsor prior to treatment	X		X ^k	X ^k	X ^k		X ^k	X ^k		
Safety Assessments	Pregnancy test (serum or urine; females of childbearing potential only)		X ^d				X				X	X ^e
	HbA1c										X	
	Physical exam		X ^d		X	X	X				X	X ^f
	Weight		X ^d				X				X	
	CBC with differential		X ^d		X ^m	X ^m	X		X ^m	X ^m	X	
	Serum chemistry panel and liver function tests		X ^d		X ^m	X ^m	X		X ^m	X ^m	X	
	Random blood glucose ^j		X		X ^j	X ^j	X		X ^j	X ^j		
	Vital signs ^l		X		X	X	X		X	X	X	
	ECOG performance status		X ^d				X				X	
	Concomitant medications	Related to study procedures	Collect from Day 1 predose to EOT or 30 days post last dose, whichever is later									
	AE collection											
Biomarker Assessments	Blood samples for biomarker assessment (see Section 7.4.1)		See Table 18									

	Assessment	Enrollment	Cycle 1				Cycle 2+				EOT	F/U
			D1	D3	D8	D15	D1	D3	D8	D15		
			Within 7D of 1st dose	± 2d ^b	+ 1d	± 2d	± 2d	± 2d	+ 1d	± 2d	Within 30–37D of last dose ^a	Every 6 or 12 weeks
	Day	Within 7D of 1st dose	D1	D3	D8	D15	D1	D3	D8	D15	Within 30–37D of last dose ^a	Every 6 or 12 weeks
	Visit window		± 2d ^b	+ 1d	± 2d	± 2d	± 2d	± 2d	± 2d	± 2d	± 3d or ± 7d	± 3d or ± 7d
	Tumor biopsy for research (see Section 7.4.2)											
PK/ATA	Samples for PK testing (see Section 7.3)		See Table 18									
	Samples for ATA testing (see Section 7.3)											
Response Assessments	CT/MRI for non-prostate cancer subjects ^g		Every 6 weeks (±3 days) for the first 12 months, then every 12 weeks (±7 days) thereafter ^h							X ⁱ	X ^f	
	CT/MRI for prostate cancer subjects ^g		Every 8 weeks (±7 days) for the first 24 weeks, then every 12 weeks (±7 days) thereafter ^h							X ⁱ	X ^f	
	Bone scan (prostate cancer subjects only) ^g		Every 8 weeks (±7 days) for the first 24 weeks, then every 12 weeks (±7 days) thereafter ^h							X ⁱ	X ^f	
	Survival follow-up contact										X ^f	

D=day, F/U=follow-up.

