a EOT evaluations should be obtained before the initiation of non-protocol therapy. If EOT evaluations are completed before 30 days following the last study treatment, conduct a phone screen 30–37 days following the subject's last study treatment to ensure that no changes in AE profile have occurred.

b Visit window does not apply to Cycle 1, Day 1.

c PSA test on Day 1 of each cycle or, once every 3 weeks (±3 days) per calendar. For F/U, PSA test every 12 weeks (±7 days).

d Not required in Cycle 1 if baseline was assessed within 3 days prior to first dose of study drug.

e Only tested once at 24 weeks after last dose of LV.

f Every 6 weeks (± 3 days) for the first 12 months after the first dose of LV, then every 12 weeks (± 7 days) thereafter. Continue to assess until disease progression. After a year of follow-up, reduce scanning frequency to institution's standard of care. For F/U in prostate cancer subjects, CT/MRI and bone scans every 12 weeks (±7 days)

g See Section 7.2.1 for tumor cohort-specific imaging requirements. Submit copies of images to independent review facility.

h If required, it is recommended that scans not be scheduled on the dosing day. It is recommended that scans done on the same day as Day 1 of subsequent cycles be completed and reviewed prior to infusion with LV.

i Not required if conducted within 4 weeks prior to EOT.

j Random blood glucose should be checked prior to dosing on Day 1 of each 21-day cycle; and on Day 8 and Day 15 of Cycle 1 and 2. Following Cycle 2, it may be checked on days 8 and 15 as indicated, particularly in subjects at risk for hyperglycemia (Section 5.6).

k A +2 day dosing window is allowed. At least 7 days must elapse between administrations of LV.

l Vital signs to be within 60 minutes prior to the start of LV infusion and within 30 minutes after completion of LV infusion

m Only required for Cycle 1 and Cycle 2.

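### From Cycle 3, Parts B and C require a neutrophil count before each Day 8 dose (and each q1wk Day 15 dose), but no blood count is scheduled on those days

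*Protocol*

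**What the plan says.** **The criterion.** Protocol Section 5.2.3.1 sets four laboratory conditions for Day 1 of each cycle (neutrophils, AST, ALT, total bilirubin). For Parts B and C it adds that neutrophils must be at least 1000/µL "prior to LV administration on Day 8 and Day 15 (if receiving q1wk dosing) of each cycle". The consequence is also stated: "If the above criteria are not met on the day of dosing, hold the LV dose until the criteria are met". Neutrophils are the only laboratory value that this section sets for the Day 8 and Day 15 doses.

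**The schedule.** The Part B Day 8 list (Section 6.3.3.3) has "CBC with differential (see Section 7.6.3; results to be submitted to iRIS), Cycles 1 and 2 only". The same restriction appears for Part B Day 15 (6.3.3.4), Part C Day 8 in all arms (6.4.3.3) and Part C Arm 3 Day 15 (6.4.3.4). Appendix C footnote m repeats it for the Day 8 and Day 15 blood-count cells: "Only required for Cycle 1 and Cycle 2". Footnote g does the same in both Appendix D tables (Arms 1 and 2; Arm 3).

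**What remains from Cycle 3.** A blood count is still listed on Day 1 of every cycle (6.3.3.1, 6.4.3.1). The predose step "Confirm subject meets dosing criteria" also stays on Day 8 and Day 15 dosing visits without a cycle limit. The SAP is written to the 22 April 2019 protocol with q3wk dosing alone and does not bear on this.

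**The concern.** Sites have two instructions that do not match. One makes a neutrophil threshold mandatory for every within-cycle dose. The other tells them that the test supplying the value is needed only in the first two cycles. A site that works from the visit list reaches a Cycle 3 Day 8 visit with a check to sign off and no same-day count to support it. A site that works from Section 5.2.3.1 has to draw a test that the schedule does not list. Practice is likely to vary across a multicenter study.

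The threshold matters for this drug:

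- With weekly LV in SGNLVA-001 (Section 1.2.4.3), Grade 3 or higher neutropenia was reported in 21.0% of subjects and febrile neutropenia as a serious event in 3.7%.
- Primary G-CSF prophylaxis is not required in Parts B and C (Section 5.4.1).
- The hematologic rules in Tables 12 and 14 call for withholding at Grades 3 and 4, and Table 12 also calls for dose reduction at Grade 4. Asymptomatic neutropenia cannot trigger these rules if no count is taken.

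**Working it through.** The plan gives no figure to reproduce. The check has two parts: setting the texts side by side, and counting the doses affected.

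**1. Criterion against schedule**

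| Dosing visit | Neutrophil criterion (5.2.3.1) | Blood count scheduled | Source |
|---|---|---|---|
| Part B Day 8 | every cycle | Cycles 1 and 2 | 6.3.3.3; App. C note m |
| Part B Day 15 | every cycle | Cycles 1 and 2 | 6.3.3.4; App. C note m |
| Part C Day 8, Arms 1 and 2 | every cycle | Cycles 1 and 2 | 6.4.3.3; App. D note g |
| Part C Day 8, Arm 3 | every cycle | Cycles 1 and 2 | 6.4.3.3; App. D note g |
| Part C Day 15, Arm 3 | every cycle | Cycles 1 and 2 | 6.4.3.4; App. D note g |
| Day 1, Parts B and C | every cycle | every cycle | 6.3.3.1; 6.4.3.1 |

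The body text and the appendices agree with each other, and both disagree with Section 5.2.3.1. Section 7.6.3 does not close the gap, because it places the laboratory tests at the time points designated in the appendices. The glucose line in the same visit lists allows collection after Cycle 2 when indicated; the blood-count line has no such provision. Part A also limits its Day 8 and Day 15 counts to Cycles 1 and 2, but gives no LV on those days, so no conflict arises there.

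**2. Planned doses with the criterion but no scheduled count**

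Inputs: 3 doses per cycle on q1wk, 2 on 2q3wk; the only scheduled count from Cycle 3 is on Day 1. Per full cycle from Cycle 3:

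- q1wk: 2 of 3 (67%)
- 2q3wk: 1 of 2 (50%)

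Over *n* cycles (*n* ≥ 2) with no skipped doses, the share of all doses is 2(*n* − 2)/3*n* on q1wk and (*n* − 2)/2*n* on 2q3wk. The documents do not say how many cycles subjects receive, so *n* is an assumption:

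| Cycles | q1wk | 2q3wk |
|---|---|---|
| 2 | 0/6 (0%) | 0/4 (0%) |
| 4 | 4/12 (33%) | 2/8 (25%) |
| 6 | 8/18 (44%) | 4/12 (33%) |
| 8 | 12/24 (50%) | 6/16 (38%) |

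**The case against.** **The two texts can both be obeyed.** The schedule says when the count is required and does not forbid it later. A careful site will see that the predose check cannot be completed for neutrophils without a result, and will draw one. This is true and lowers the practical risk. It does not remove the fault: the check names a criterion but supplies no value, and the same list tells staff that the test is not needed.

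**Some monitoring remains.** A Day 1 count is taken every cycle, and Section 3.2.5 reports that most clinically significant neutropenia at 1.5 mg/kg q1wk followed three weekly doses, a point that the next Day 1 count comes after. But Section 5.2.3.1 judges each dose on its own day, so a Day 1 result does not satisfy it for Day 8 or Day 15.

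**Skipped doses would lower the q1wk percentages.** Section 3.2.5 says that at 1.25 mg/kg q1wk in breast cancer, dosing fell to about 2 doses per cycle from Cycle 2. Assume 3 doses in Cycle 1, then Day 1 plus one other dose per cycle. The share becomes (*n* − 2)/(2*n* + 1): 2/9 (22%) at 4 cycles, 4/13 (31%) at 6 and 6/17 (35%) at 8. This is a fair sensitivity range. It leaves the per-cycle count of planned doses unchanged.

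**There is no effect on the primary endpoint or its analysis.** None is claimed; the issue is dosing safety and consistent conduct.

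**Conclusion.** The concern holds. Section 5.2.3.1 and the schedule of events give conflicting requirements from Cycle 3 in every arm of Parts B and C, and no other text resolves the conflict. It affects 2 of 3 planned q1wk doses and 1 of 2 planned 2q3wk doses in each full cycle from Cycle 3. The share of all doses depends on time on treatment and on skipped doses. For q1wk at 6 cycles it is 44% with none skipped and 31% under the reduced-dosing assumption above; it is nil for anyone who stops by the end of Cycle 2. These figures count doses with no scheduled test. They do not estimate how many doses would be given without a count, which the documents cannot tell us. Because a mandatory safety criterion for a myelosuppressive drug is involved, this should be fixed, even though an attentive site can work around it.

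**What to change.** Let Section 5.2.3.1 govern and bring the schedule into line with it:

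1. In Sections 6.3.3.3, 6.3.3.4 and 6.4.3.3, and in the Arm 3 list of 6.4.3.4, delete the Cycles 1 and 2 restriction from the blood-count line. A count with differential is then required before each Day 8 LV dose (Part B, all Part C arms) and each Day 15 LV dose (Part B, Part C Arm 3) in every cycle.
2. In Appendix C, remove footnote m from the Day 8 and Day 15 blood-count cells.
3. In Appendix D, remove footnote g from the Day 8 blood-count cell for Arms 1 and 2, and from the Day 8 and Day 15 blood-count cells for Arm 3.

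The limits on chemistry and liver tests, and on the non-dosing Day 15 count in Arms 1 and 2, can stay, since Section 5.2.3.1 does not call for those.

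The cost is wording in four visit lists and three tables, plus a routine local blood count at existing dosing visits: from Cycle 3, 2 more per cycle on q1wk and 1 more on 2q3wk. As the lines now read, each added result would also go to iRIS; the sponsor could waive that for later cycles. If the sponsor prefers less testing, the alternative is to limit the Day 8 and Day 15 criterion itself to Cycles 1 and 2 with a stated safety rationale. Either way, the two texts must agree.
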